13.2. Monitoring for Adverse Events

At each visit, after the subject has had the opportunity to spontaneously mention any problems, the Investigator should inquire about AEs by asking if the patient has any problems.

13.3. Procedures for Recording and Reporting AEs and SAEs

Subsequent to signing an informed consent form, all untoward medical occurrences that occur during the course of the study must be documented on an Adverse Event Form (AEF). A separate AEF must be filled out for each event. When possible, signs and symptoms indicating a common underlying pathology should be documented as one comprehensive event. For each recorded event, the AE documentation must include the onset date, outcome, resolution date (if event is resolved), intensity (i.e., severity), any action with study treatment taken as a result of the event, and an assessment of the adverse event's relationship to the study treatment.

Nonserious Adverse Events

A nonserious AE is defined as any untoward change in a subject's medical health that does not meet serious criteria noted below (e.g., is not life-threatening, does not require hospitalization, does not prolong a current hospitalization, is not disabling, etc.). All adverse events must be reported regardless of whether or not they are related to the study treatment.

For nonserious adverse events, an AEF containing all available information will be collected on a routine basis and submitted to the Medical Monitor at the close of the study.

Serious Adverse Events

A serious adverse event (SAE) is defined as any adverse experience that meets any of the following criteria:

• Results in death.

• Is life-threatening.

NOTE: Life-threatening means that the subject was at immediate risk of death from the reaction as it occurred; i.e., it does not include a reaction which hypothetically might have caused death had it occurred in a more severe form.

- Requires inpatient hospitalization or prolongation of existing hospitalization. NOTE: In general, hospitalization signifies that the individual remained at the hospital or emergency ward for observation and/or treatment (usually involving an overnight stay) that would not have been appropriate in the physician's office or an out-patient setting. Complications that occur during hospitalization are AEs. If a complication prolongs hospitalization or fulfills any other serious criteria, the event is serious. When in doubt as to whether "hospitalization" occurred, the event should be considered serious.
- Results in persistent or significant disability/incapacity. Disability is defined as a substantial disruption of a person's ability to conduct normal life functions. NOTE: The term disability means a substantial disruption of a person's ability to conduct normal life functions. This definition is not intended to include experiences of relatively minor medical significance such as uncomplicated headache, nausea, vomiting, diarrhea, influenza, or accidental trauma (e.g., sprained ankle) which may interfere or prevent everyday life functions but do not constitute a substantial disruption.
- Is an important medical event. An important medical event is an event that may not result in death, be life-threatening, or require hospitalization but may be considered an SAE when, based upon appropriate medical judgment, it may jeopardize the subject and may require medical or surgical intervention to prevent one of the outcomes listed in the definitions for SAEs. Examples of such medical events include allergic bronchospasm requiring intensive treatment in an emergency room or at home, blood dyscrasias or convulsions that do not result in subject hospitalization, or the development of drug dependency or drug abuse.

All available information on a serious adverse event(s) and any other associated AE, if applicable, must be forwarded to the study coordinator for forwarding to the Medical Monitor immediately (i.e., within one working day of the Investigator's or site's knowledge of the event) as follows:

- In studies utilizing EDC (electronic data capture), all available information for the SAE and any associated AE(s) must be entered immediately into the EDC system.
- Additional information for any applicable event is to be reported as soon as it becomes available.

In addition to the reporting of serious adverse events to the study Medical Monitor, the SAE must be reported to the IRB / IEC according to their requirements.

The investigator must document all adverse device events (serious and nonserious but related) and all serious adverse events (related and unrelated) on the Adverse Device Effect and Serious Adverse Event Form. Any device quality complaints will also be documented.

- Both the Quality Complaint Form and the Adverse Device Effect and Serious Adverse Event Form must be e-mailed immediately to the study coordinator ([name]).
- Additional relevant information is to be reported as soon as it becomes available.

12.3.1 Intensity and Causality Assessments

For every adverse event and quality complaint, the investigator must assess the causality as Related or Not Related to the medical device under investigation. An assessment of causality will also be performed by the Medical Monitor utilizing the same definitions, as shown below:

Causality

- Related An adverse event or quality complaint classified as related may be either definitely related or possibly related where a direct cause and effect relationship with the medical device has not been demonstrated, but there is a reasonable possibility that the adverse event or quality complaint was caused by the medical device.
- Not Related An adverse event or quality complaint classified as not related may either be definitely unrelated or simply unlikely to be related (i.e., there are other more likely causes for the adverse event or quality complaint).

Where appropriate, the investigator must assess the intensity (severity) of the adverse event as mild, moderate, or severe based on medical judgment with consideration of any subjective symptom(s), as defined below:

Intensity (Severity)

vent is mild if the subject is aware of but can easily
ign or symptom.
vent is moderate if the sign or symptom results in
gnificant enough to cause interference with the
al activities.
vent is severe if the sign or symptom is incapacitating the subject's inability to work or engage in their es.

The investigator must document any action taken (i.e., medication, intervention, or treatment plan) and outcome of the adverse event or quality complaint when applicable.

13.4. Follow-Up of Adverse Events and Quality Complaints

The investigator is responsible for adequate and safe medical care of subjects during the study and for ensuring that appropriate medical care and relevant follow-up procedures are maintained after the study. Any additional data from these follow-up procedures must be documented and available to the study coordinator who, with the Medical Monitor, will determine when the data need to be documented on the CRFs.

13.5. Safety Analyses

The type, severity, duration and frequency of reported ocular adverse events will be tabulated. Adverse events will also be summarized for events that were considered treatment-related.

14. GCP, ICH and ETHICAL CONSIDERATIONS

This study will be conducted in compliance with Good Clinical Practices (GCPs), including International Harmonization (ICH) Guidelines, and in general, consistent with the 1996 version of the Declaration of Helsinki. In addition, all applicable local, state and federal requirements will be adhered to.

This study is to be conducted in accordance with Institutional Review Board regulations. The investigator will obtain appropriate IRB/ethics committee approval prior to initiating the study.

The study will be registered with clinicaltrials.gov.

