10. ANALYSIS PLAN

10.1. Analysis Data Sets

All subjects who are enrolled in the study will be evaluated for safety. Efficacy analyses will be performed based on data from those eyes with uncomplicated LASIK surgery.

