10.2. Statistical Methodology

A summary of the data will be prepared for all measurement time points.

For variables measured on a continuous scale, these summaries will include the sample size, as well as the mean, standard deviation, median, minimum, and maximum. For variables measured on a categorical scale, summaries will provide the number and percentage of subjects in each category. These summaries will be provided for all eyes completing the study.

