15. STANDARD EVALUATION PROCEDURES

Table 15.1. Proposed Visits and Study Assessments

(visits are by patient, with both eyes tested)

Activity	Pre- operative	Operative	Postoperative		
,	Visit 1	Visit 2	Visit 3	Visit 4	Visit 5
			1 Week	1 Month	3 Months
Informed Consent	Х				
Demographics	Х				
General Information: Medical History	Х				
Surgery		Х			
Manifest refraction	Х			Х	Х
Monocular uncorrected distance VA	Х		Х	Х	Х
Monocular corrected distance VA	Х			Х	X
Slit Lamp Exam	Х		Х	Х	X
Dilated Fundus Exam	Х				X
Topography (Vario and iTrace)	Х				X
Aberrometry (Vario and iTrace)	Х				Х
PROWL Questionnaire	Х				Х
OSDI Questionnaire	Х				Х
Complete Exit Form ¹	Х				Х

¹ Complete Exit Form upon termination of subject participation, or at Visit 5, whichever occurs first.

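### The planned safety tables omit non-ocular events judged unrelated, and no planned output counts the eyes that lost corrected acuity

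*Combined protocol and SAP*

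**What the plan says.** **Adverse events.** Section 13.5 (Safety Analyses) states: "The type, severity, duration and frequency of reported ocular adverse events will be tabulated". It adds: "Adverse events will also be summarized for events that were considered treatment-related". These are the only adverse event outputs planned. Collection is wider. Section 13.3 states: "All adverse events must be reported regardless of whether or not they are related to the study treatment". It also requires documentation of "all serious adverse events (related and unrelated) on the Adverse Device Effect and Serious Adverse Event Form", quick forwarding to the Medical Monitor, and notice to the ethics board: "the SAE must be reported to the IRB / IEC according to their requirements". Section 10.1 sets the safety population: "All subjects who are enrolled in the study will be evaluated for safety".

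**Corrected acuity.** Table 15.1 lists "Monocular corrected distance VA" before surgery (Visit 1), at 1 month (Visit 4) and at 3 months (Visit 5). It is not named as a primary, secondary, exploratory or safety variable in Sections 3, 8.1 or 13.5. Two general rules cover it. Under Section 10.2, for continuous variables, "these summaries will include the sample size, as well as the mean, standard deviation, median, minimum, and maximum", and this is done for eyes that complete the study. Section 10.2.1 adds a paired t-test. No change-per-eye table and no loss threshold is given.

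**The concern.** The plan promises a safety evaluation of everyone enrolled and gathers the data for it, but the tables it specifies are narrower than both the population and the data. A reader of the final report could not see the full set of serious events, and could not see how many eyes ended with worse corrected vision than they started with. In an elective procedure on eyes that must already correct to 20/20 or better, that second number is the most direct measure of visual harm in this data set. A group mean cannot supply it. The eyes most likely to have lost vision are also those that the plan's inclusion rules can remove.

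**Working it through.** The plan gives no safety figure to reproduce. Its sample size calculation concerns satisfaction and has no bearing here.

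**1. Which events reach a table (Section 13.5)**

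| Event | Ocular table | Treatment-related summary |
|---|---|---|
| Ocular, related | yes | yes |
| Ocular, unrelated | yes | no |
| Non-ocular, related | no | yes |
| Non-ocular, unrelated | no | no |

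The last row is empty whether or not the event is serious. Seriousness is not a dimension of either output: the severity in Section 13.5 is the mild, moderate or severe grade defined in Section 12.3.1 (printed within Section 13). That section also judges causality against the medical device, while Section 13.5 speaks of treatment. The filter for non-ocular events is therefore not fully defined.

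**2. What the acuity summaries can show**

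Inputs from the plan: 104 eyes of 52 subjects (Section 7.1), and baseline corrected acuity of 0.00 logMAR or better in each eye (Section 7.2). Assumptions, not in the plan: a loss of 0.20 logMAR as the threshold, 3 affected eyes, and the behaviour of the other eyes.

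- Share of eyes affected: 3/104 = 2.9%.
- Other 101 eyes gain 0.02 logMAR: mean change = (3 × 0.20 − 101 × 0.02)/104 = (0.60 − 2.02)/104 = −0.014, an improvement.
- Other eyes unchanged on average, SD of change 0.05: mean change = 0.60/104 = 0.0058. The SD over all eyes is about 0.060, so t = 0.0058/(0.060/√104) ≈ 0.98 and p ≈ 0.33, treating eyes as independent.
- Visit 5 maximum: because every eye starts at 0.00 or better, a value above 0.00 shows that at least one eye lost acuity. It does not say how many. An eye going from −0.20 to 0.00 loses 0.20 and still sits at the entry limit, so the maximum does not flag it.

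**3. Which eyes are in the summaries**

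- Section 10.2 restricts them to completing eyes.
- Section 9.2.2 allows performance data to be left out when surgery was not completed successfully, and Section 10.1 limits efficacy analyses to uncomplicated eyes. The plan does not say whether corrected acuity counts as efficacy or safety.
- Section 18.3 terminates subjects with a severe, possibly related event and counts them as completers, while Section 18.1 ties completion to Visit 5. On either reading such a subject may have no Visit 5 acuity.

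**4. What a count would support**

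If no eye met the threshold, the exact two-sided 95% upper limit is 1 − 0.025^(1/n):

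- 104 eyes taken as independent: 1 − 0.025^(1/104) = 3.5%.
- 52 subjects: 1 − 0.025^(1/52) = 6.8%.

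Two eyes of one subject are not independent, so the subject-level limit is the safer one to report. These limits describe the precision available at this sample size. They do not measure the gap itself.

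**The case against.** The strongest case against rests on what the plan does cover. Every serious event, related or not, is documented on a dedicated form and sent to the Medical Monitor and the ethics board. All ocular events are tabulated whatever their cause. Related is defined broadly enough to include possible relation, and the Medical Monitor makes a second assessment. An acuity loss recorded as an adverse event would appear in the ocular table. The paired acuity data are used, through the t-test in Section 10.2.1, and the baseline limit gives the Visit 5 maximum some power to reveal a loss.

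All of this stands, and it rules out three stronger readings that a reader might infer:

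- That serious events would go unreported. Section 13.3 says otherwise; they are absent only from the planned tables.
- That the paired acuity is never used. It is, for a mean change.
- That leaving out unrelated non-ocular events makes the safety results favourable. Nothing in the documents shows this, and for a local eye procedure in 52 subjects the effect may be small. Lack of masking adds little, since a single-arm study has no allocation to mask.

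What the objection does not remove: individual case reporting is not a presentation of results, a mean change is not a count, and no section says how much acuity loss must be recorded as an adverse event, so capture by that route depends on judgement.

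**Conclusion.** Two gaps hold. Non-ocular events judged unrelated, including serious ones, are in no planned safety table, although they are collected and the safety population is everyone enrolled. No planned output counts eyes that lost corrected acuity, and eyes with complicated surgery or early exit can fall out of the summaries that exist. The acuity gap is the more important of the two.

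The size can only be illustrated: 2.9% of eyes could lose 0.20 logMAR while the mean improves by 0.014. That rests on an assumed 3 affected eyes, an assumed gain of 0.02 in the rest, and a threshold that the documents do not give. No size can be put on the adverse event gap. This is a cheap improvement to the safety reporting. It does not affect the primary analysis or the sample size.

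**What to change.** In Section 13.5:

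- Tabulate all adverse events in all enrolled subjects: ocular events by eye and by subject, non-ocular events by subject. List every serious event regardless of relatedness. State whether relatedness is to the device or to the treatment.
- Add the number and percentage of eyes, and of subjects with at least one eye, whose corrected acuity fell by a prespecified amount from Visit 1 to Visit 5. A loss of 0.20 logMAR or more is one possible threshold, offered here as a proposal.
- Include all operated eyes. Where Visit 5 is missing, use the last available postoperative corrected acuity, and show how many eyes have no Visit 5 value, since an earlier value may reflect a temporary loss.
- Give an exact 95% confidence interval at subject level.

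Sections 9.2.3 and 9.3.2 imply corrected acuity at 1 week, while Table 15.1 does not mark it. These must be reconciled, because they decide which earlier values exist.

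The cost is two or three extra tables and the programming for them. No new data, visits or subjects are needed.

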15. STANDARD EVALUATION PROCEDURES

Table 15.1. Proposed Visits and Study Assessments

(visits are by patient, with both eyes tested)

Activity	Pre- operative	Operative	Postoperative		
,	Visit 1	Visit 2	Visit 3	Visit 4	Visit 5
			1 Week	1 Month	3 Months
Informed Consent	Х				
Demographics	Х				
General Information: Medical History	Х				
Surgery		Х			
Manifest refraction	Х			Х	Х
Monocular uncorrected distance VA	Х		Х	Х	Х
Monocular corrected distance VA	Х			Х	X
Slit Lamp Exam	Х		Х	Х	X
Dilated Fundus Exam	Х				X
Topography (Vario and iTrace)	Х				X
Aberrometry (Vario and iTrace)	Х				Х
PROWL Questionnaire	Х				Х
OSDI Questionnaire	Х				Х
Complete Exit Form ¹	Х				Х

¹ Complete Exit Form upon termination of subject participation, or at Visit 5, whichever occurs first.

17. FINANCIAL AND INSURANCE INFORMATION/STUDY RELATED INJURIES

Every effort to prevent study-related injury will be taken by the Study Doctor and staff. In the event a patient is injured as a direct result of the study while following the Study Doctor's instructions and the study requirements, the patient will be instructed to contact his or her doctor immediately. The Study Doctor is to treat the injured subject as needed for those injuries caused directly by this research study. In the event of injury or illness caused by or occurring during a subject's participation in this research study, all charges for medical care provided to the subject will be billed to his or her insurance company. The Study Doctor or Sponsor does not offer to cover the medical care costs for injuries or illnesses that are not caused directly by the research study. The Sponsor does not offer to provide any other compensation, unless specifically agreed to elsewhere in this document. This information will be provided to each study subject before the start of the study in the consent form.

18. STUDY ENDPOINT CRITERIA

18.1. Patient Completion of Study

If a study patient has completed the final visit (Visit 5) of the study, he/she is considered to have completed the study.

18.2. Patient Discontinuation

Each study patient may voluntarily discontinue the study at any time they choose. Study patients who cannot complete the study for administrative reasons (e.g., non-compliance, failure to meet visit schedule, etc.) will be discontinued from the study. Study patients discontinued during the enrollment phase (prior to surgery) of the study will be replaced.

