9.2. Visits and Examinations

Subjects will participate in 3 study visits, including one visit for bilateral surgery. Visits will include an uptake visit, and one operative visit (Visit numbers 1-2 below). The visit schedule, complete with window and associated CRF forms, are displayed in Table 9.2-1. Details of each study visit, including testing to be conducted, are provided below.

Visit Number	Visit Name	Visit Window	CRF Number
1	Preoperative	-90 to 0 days from surgery	1
2	Operative	0 from surgery	2
3	1 Week Postoperative	7 (±3) days postoperative	3
4	1 Months Postoperative	30 (±7) days postoperative	4
5	3 Months Postoperative	90 (±20) days postoperative	5

Table 9.2-1. Visit Schedule

v 1.0

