9.2.4. Postoperative 3 Month

All routine, usual standard of care postoperative measures should be undertaken. In addition, the subject will undergo VA, manifest refraction, slit lamp examination, dilated fundus exam, topography, aberrometry, and complete the OSDI and PROWL questionnaires (Section 9.3). Any device deficiencies or adverse events will be monitored.

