9.5. Discontinued Subjects

Discontinued subjects are those who do not have an exit visit or who come into the office to be exited prior to the scheduled final study visit. Subjects may be discontinued from the study at any time if, in the opinion of the investigator, their continued participation in the study poses a risk to their health. The reasons for discontinuation include:

- a. Adverse event;
- b. Lost to follow-up;
- c. Subject decision unrelated to an adverse event;
- d. Protocol violation;
- e. Treatment failure;
- f. Other.

To ensure the safety of all subjects who discontinue prior to Visit 5, investigators should assess each subject and, if necessary, advise them of any therapies and/or medical procedures that might be needed to maintain their health. Any changes in medical health and/or use of concomitant medications should also be captured.

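### Section 18.2's administrative discontinuation rule does not exempt operated subjects, so it can be applied in a way that loses the only postoperative PROWL Q1

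*Combined protocol and SAP*

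**What the plan says.** Section 18.2 (Patient Discontinuation) contains the rule: "Study patients who cannot complete the study for administrative reasons (e.g., non-compliance, failure to meet visit schedule, etc.) will be discontinued from the study". The next sentence deals with replacement, but only before surgery: "Study patients discontinued during the enrollment phase (prior to surgery) of the study will be replaced".

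Section 18.1 defines completion by one visit: "If a study patient has completed the final visit (Visit 5) of the study, he/she is considered to have completed the study". Section 9.5 defines the opposite group, with Visit 5 as the reference point at the end of the sentence: "Discontinued subjects are those who do not have an exit visit or who come into the office to be exited prior to the scheduled final". It then gives the investigator a permissive power based on risk to health: "Subjects may be discontinued from the study at any time if, in the opinion of the investigator" judges that continuing poses such a risk.

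The visit schedule in Table 9.2-1 gives every visit a window. The 1-month visit, for example, is set at "30 (±7) days postoperative"; the 1-week visit is day 7 ±3 and the 3-month visit is day 90 ±20.

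After surgery, the subject is asked to "complete the OSDI and PROWL questionnaires" only at the 3-month visit (section 9.2.4, Postoperative 3 Month), and Table 15.1 agrees. On the analysis side, section 10.2 says: "These summaries will be provided for all eyes completing the study".

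**The concern.** The intervention is one bilateral operation on day 0. After that there is no study treatment to stop, so discontinuing a subject for an administrative reason does nothing except end data collection. The primary outcome, PROWL Q1, has a single postoperative measurement, at Visit 5. A subject exited between surgery and Visit 5 therefore contributes nothing to the primary percentage, even if willing and able to attend at 3 months.

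The study is single-arm and reports one satisfaction percentage, so there is no comparison group in which a similar loss might offset the effect. Keeping appointments may well be related to satisfaction, and in either direction: contented patients may skip early checks, and unhappy ones may stop complying or go elsewhere. Section 10 describes no method for missing outcomes. Avoidable, non-random loss would pass directly into the headline result.

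**Working it through.** **1. What the rule covers.** Three provisions have to be read together.

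- 18.2 is mandatory in tone. It is aimed at patients who are unable to complete, and it gives non-compliance and not keeping to the visit schedule as examples of the reason. It does not say which visits count, how many, or whether surgery changes anything.
- 18.1 asks only whether Visit 5 was completed. Visits 3 and 4 are not conditions, and no window is mentioned.
- 9.5 counts as discontinued anyone without an exit visit or exited before the final visit.

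On a reading led by 18.1, a subject who misses Visit 3, or has Visit 4 on day 40 (window: day 23 to 37), can still complete and lies outside 18.2. On a reading led by the examples in 18.2, the same subject has not kept to the schedule and is to be exited. Section 18.1 protects only a subject who is allowed to reach Visit 5, and 9.5 then simply describes the exit. No sentence chooses between the two readings.

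**2. What an exit would cost.**

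| Outcome | Postoperative collection | Effect of exit before Visit 5 |
|---|---|---|
| PROWL Q1 (primary) | Visit 5 only | No 3-month value |
| PROWL Q2-Q33, OSDI, aberrometry (exploratory) | Visit 5 only | No 3-month value |
| Spherical equivalent (secondary) | Visits 4 and 5; also Visit 3 in the section 9.2 text, though not in Table 15.1 | Less exposed: no visit is named for the endpoint and a 1-month refraction may exist |

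The Exit Procedures section asks for the study examinations at premature exit if they can be done. At best this gives an early value, not the 3-month outcome. There is no instruction to return at 3 months.

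**3. The plan's own figure.** Section 11 gives 46 pairs for 90% power at 5%, with a mean difference of 25 points and an SD of differences of 50, so d = 25/50 = 0.5.

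- Normal approximation, two-sided: n = ((1.960 + 1.282) × 50/25)² = 42.03, rounded up to 43.
- Paired t-test (noncentral t), two-sided: n = 44, power 90.0%. At n = 46, power is 91.3%.

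The stated 46 is therefore reproduced to within 2 subjects. The dropout allowance is 52 − 46 = 6, and 6/52 = 11.5%.

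**4. How many could be exposed (assumed rates).** The documents give no missed-visit rate. Suppose each of the two interim visits is missed or out of window independently with probability p. The chance of at least one is 1 − (1 − p)².

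| p (assumed) | 1 − (1 − p)² | × 52 |
|---|---|---|
| 3% | 5.9% | 3.1 |
| 5% | 9.75% | 5.1 |
| 10% | 19.0% | 9.9 |

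These are subjects to whom the stricter reading could be applied, not predicted losses.

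**5. Effect on the percentage.** If k of 52 have no Q1, the full-cohort percentage can lie anywhere in a range of width k/52. For k = 3, 5, 6 and 10 the widths are 5.8, 9.6, 11.5 and 19.2 percentage points. Example with an assumed count: if 6 are lost and 42 of 46 are satisfied, the report reads 91.3%, while the value for all 52 lies between 42/52 = 80.8% and 48/52 = 92.3%.

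**6. Effect on power (assumed removals, same paired t-test, n rounded down).**

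| Removed by the rule | No other dropout: n, power | On top of the 11.5% allowance: n, power |
|---|---|---|
| 5% | 49, 92.9% | 43, 89.3% |
| 10% | 46, 91.3% | 41, 87.8% |
| 15% | 44, 90.0% | 39, 86.1% |
| 20% | 41, 87.8% | 36, 83.1% |

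The loss of power is modest. Selective exclusion is the more important effect.

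**The case against.** The strongest reply is that 18.2 applies only to patients who cannot complete, that 18.1 defines completing as attending Visit 5, and that 9.5 is consistent with this. A subject who misses an interim visit but comes at 3 months is then a completer, and nothing is lost. That is a fair reading and probably the better one. It stands to this extent: the text does not compel the loss. It does not remove the point, because the protocol never says so, and a site could follow the mandatory wording and its examples instead.

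The reply also disposes of several stronger conclusions that a reader might draw.

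- A reader might infer that 18.2 requires every subject who misses a visit window to be exited. The rule is limited to those unable to complete.
- A reader might infer that a Visit 5 on day 112, just beyond day 110, leads to exclusion. Section 18.1 sets no window, so that subject is a completer. What is missing is a statement of how the late value is analysed.
- A reader might infer that the secondary endpoint is lost in the same way. Its visit is not named, and refraction is also taken at 1 month.
- A reader might infer that an exited subject is left without examination. The Exit Procedures section and sections 9.5 and 13.4 provide for examination at exit, assessment and follow-up care, though not for a 3-month questionnaire.

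It is also true that the bounds in the working would be the same for any six subjects lost for any reason. They show what a loss does to the percentage, not how often 18.2 would cause one.

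**Conclusion.** The point holds as a gap in the rule that should be closed, not as a rule that makes data loss certain. Section 18.2 directs administrative discontinuation, gives no threshold and does not exempt operated subjects. If it is applied after surgery to someone who could still attend Visit 5, that subject has no 3-month PROWL Q1, has no stated replacement and leaves the completer summaries, for no gain, since no treatment remains to be stopped.

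The direction of any bias is unknown. So is its size: the missed-visit rates, their independence and the count of satisfied subjects used above are all assumptions. Each subject lost adds 1/52 = 1.9 percentage points to what cannot be known about the full-cohort percentage, and at the assumed rates the 6-subject allowance could be used partly or wholly on subjects who were still available. The secondary endpoint is less exposed.

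**What to change.** - In 18.2, limit administrative discontinuation, with replacement, to subjects not yet operated.
- For operated subjects, record a missed or out-of-window visit, or other non-compliance, as a protocol deviation, and still ask the subject to attend Visit 5.
- In section 10, include a Visit 5 outside 90 ±20 days in the main analysis, flagged, and add a sensitivity analysis limited to in-window visits.
- Leave voluntary withdrawal (18.2) and the safety provisions in 9.5 and 18.3 unchanged. Wording under which an operated subject could leave only by withdrawing consent or being lost to follow-up would conflict with those provisions and should not be used.
- Reconcile 18.1, 18.2 and 9.5 so that completed and discontinued mean the same thing throughout.

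The cost is a wording change, some out-of-window data and a few more deviations to log. No visits or subjects are added.
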